10.4 Proposed Data Analysis

At study completion a one-sided one sample exponential test will be conducted to detect an increase above the presumed historical control rate of 65% PFS at two years. If this test is rejected at $\alpha = .10$, the treatment regimen will be considered sufficient for further investigation. Probabilities of times to local recurrence, regional recurrence and death will be estimated by the Kaplan-Meier method with 95% confidence intervals as well as by cumulative incidence if needed to adjust for the competing risk of death. Treatment-related toxicities will be summarized by frequency and grade. If intervening deaths are observed cumulative incidence plots and analysis of competing risks may be conducted.

A series of correlative studies will be conducted based on blood and tissue samples collected prior to treatment among patients treated with pembrolizumab + ISA101b. The first item below is a planned analysis with alpha spending of 10% to be distributed among the biomarker endpoints.

1. Test the association of baseline H score of PD-L1 tumor expression, circulating antibodies against HPV, EGFR and p53 and other tumor antigens upon PFS using proportional hazards regression adjusting if needed for confounding variable such as T stage, N stage and smoking history.
2. Estimate and test the effect of ISA101b using paired (pre/post pembrolizumab +/- ISA101b) values of immune and inflammatory makers will be compared with the Wilcoxon test.
3. Compare differences in circulating HPV, EGFR, p53 and other tumor antigen antibodies using baseline versus 3-6 weeks or 6 months post-treatment. Linear mixed effect models will be used to evaluate the longitudinal response.
4. Estimate and characterize sequential series of blood samples pre- and post-treatment for a series of immune and inflammatory markers. These will be specified by the investigator and due to exploratory nature of these additional tests, p values will be adjusted for false discovery.

The change in CD4, CD8, FOXP3, PD-1, PD L1, and PD-L2 over time will be described graphically. An exploratory analysis of the relationship between those changes and PFS will be conducted by proportional hazards regression.

To define the neoepitope landscape and to delineate alterations in transcriptomic signature, we will complete whole exome sequencing (WES) and RNA-Seq on all 45 patients who receive pembrolizumab. Fisher's Exact test will be used to compare mutational burdens and differences in the frequency of nucleotide changes. Differentially

expressed genes will be identified and differences between treatment groups and clinical response groups will be explored. Log-rank tests will be used to compare Kaplan-Meier curves, and the relationship with PFS will be further characterized by proportional hazards (Cox) regression.

To define the alterations in TCR clonality between matched baseline and Week 2 CRT biopsies from this trial, we will use the ImmunoSeq assay from Adaptive Biotechnologies to sequence TCR beta chains. Differences in TCR clonality between treatment groups and clinical response groups will be explored using Fisher exact test.

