1.2 HPV and Head and Neck Cancer Survival

HPV(+) HNSCC is rapidly increasing in incidence.⁷ In the US, two-thirds of patients with oropharynx cancer have HPV(+) tumors. HPV status and pack-years of tobacco exposure are the major determinants of OS in HNSCC, followed by nodal stage.⁸ Based upon HPV status, pack-years and nodal stage, patients with HNSCC can be classified patients into three risk groups having low, intermediate, or high risk of death. This clinical risk classification has framed national clinical trial priorities in PULA HNSCC. Specifically, de-intensification strategies are being tested in patients with low-risk HPV(+) HNSCC whereas intensification strategies are the major unmet need for high-risk HPV(-) and intermediate-risk HPV(+) disease.^{9,10}

Tumor HPV status has been shown to be a strong, independent prognostic biomarker for patients with HNSCC treated with cisplatin- or cetuximab-based RT. Patients with HPV-positive OPSCC have a 58% (HR 0.42, 95%CI 0.27-0.66) reduction in risk of death when compared to patients with HPV-negative OPSCC, after adjustment for other prognostic factors. HPV-positive cancers have been shown to have higher response rates to chemotherapy and CRT, resulting in higher local-regional disease control. Furthermore, the combination of HPV status, pack-years of tobacco smoking, and tumor stage has been shown to classify patients as having a low, intermediate, or high risk of death. Three-year rates of OS were 93% (95%CI, 88.3-97.7) in the low-risk group, 70.8% (95%CI 60.7-80.8) in the intermediate-risk group, and 46.2% (95%CI 34.7-57.5) in the high-risk group. Novel therapies are thus needed in both intermediate and high-risk patients to improve both local-regional control and reduce risk of distant metastases.

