6.1.3.7 Time to Progression and Progression-free survival

This interval will be measured from the date of entry on the study to the appearance of new metastatic lesions or objective tumor progression.

Progression-free survival (PFS) will be calculated from treatment initiation to disease progression or death from any cause or last follow up.

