8.4 Long Term Follow Up

After completion of IMRT, patients will be evaluated radiographically and clinically as per standard of care. This would be every 3 months for 12 months (+/- 2 weeks), then every 6 months (+/- 1 month) for one year, then annually (+/- 1 month) for three years, which will represent a total of 5 years from completion of IMRT. Other evaluations will start approximately 6 months after completion of IMRT, and will include the following:

- History and physical examination and performance status
- Vitals signs, including weight
- Assessment for late toxicity, including dysphagia, xerostomia, gastrostomy tube dependence, pain, fibrosis and lymphedema within the head and neck, hypothyroidism, late autoimmune events
- Thyroid function testing (TSH, FT4)
- Complete blood count, including platelets and differential
 - Blood chemistries (may be obtained from whole blood or serum/plasma sample), including
 - BUN, glucose, uric acid, lactate dehydrogenase, creatinine, electrolytes (K⁺, Na⁺, Cl⁻, CO₂), calcium, Mg⁺⁺ and liver function tests [bilirubin, AST (SGOT), ALT (SGPT), and alkaline phosphatase, total protein, albumin]
- Research blood collection (6, 9, 12, 18, 24, 36, 48, and 60 months after completion of radiotherapy +/- one month)
- During the long term follow-up period, tumor assessments using anatomic imaging (CT or MRI) will be performed 6, 9, 12, 18, 24, 36, 48, and 60 months after completion of radiotherapy (+/- one month). The minimum protocol imaging requirement is: contrasted, diagnostic neck and chest CT at intervals specified above. More intensive imaging may be conducted per local practice.
- Swallowing assessments per local practice and as indicated by post-radiotherapy evaluation and patient-reported symptoms
- Note: patients who have documented progression may discontinue scheduled study assessments and will be followed only for survival. Survival assessments will be performed every 6 months (+/- 2 months) by telephone contact and/or by evaluation of the Social Security Death Index or other public records.
- Note: should tumor recurrence be pathologically documented at any time, a sample of the diagnostic specimen should be submitted for correlative studies.

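### Kaplan-Meier is the firm estimator for local and regional recurrence, cumulative incidence is optional, and only death is named as competing: a modest upward bias outside the primary test

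*Combined protocol and SAP*

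**What the plan says.** Section 10.4 sets the estimator: "Probabilities of times to local recurrence, regional recurrence and death will be estimated by the Kaplan-Meier method with 95% confidence intervals". The sentence continues "as well as by cumulative incidence if needed to adjust for the competing risk of death", and the same paragraph adds: "If intervening deaths are observed cumulative incidence plots and analysis of competing risks may be conducted". Kaplan-Meier is thus the firm method and cumulative incidence an option. Both conditional clauses turn on death. The section gives no censoring rule for the recurrence curves and does not say which estimate is reported if both are made.

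Section 8.4 provides that "patients who have documented progression may discontinue scheduled study assessments and will be followed only for survival". The provision applies to progression of any kind, including distant failure.

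Distant failure is not in the Section 10.4 list. It enters only through progression. Section 6.1.3.7 defines time to progression thus: "This interval will be measured from the date of entry on the study to the appearance of new metastatic lesions or objective tumor progression". It defines the primary endpoint thus: "Progression-free survival (PFS) will be calculated from treatment initiation to disease progression or death from any cause or last follow up". Section 1.2 gives the clinical need as "to improve both local-regional control and reduce risk of distant metastases".

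**The concern.** A Kaplan-Meier curve for one failure type removes patients at other failures as if they could still have the event later at the same rate as those who remain. That is not the probability a reader takes from a recurrence rate.

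The plan sees this for death but not for other failures. Take a patient who is alive with distant metastases and whose scheduled scans have stopped. No death has intervened, so neither conditional clause is triggered, and the patient leaves the local-recurrence curve as ordinary censoring. The same holds for regional failure relative to local failure, and the reverse. Using the option in full would not cure this, because it adjusts for death only.

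Two things are at stake. The reported local and regional rates may be somewhat too high, and in an open-label single-arm trial the estimator can be chosen after the data are seen. In addition, one of the two failure patterns that the rationale hopes to reduce has no planned estimate of its own.

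**Working it through.** **Direction.** At each recurrence time the Aalen-Johansen estimator adds S(t−) × d/n, where S is the proportion free of every failure type. One minus Kaplan-Meier adds S_k(t−) × d/n with the same d/n, but S_k does not fall at competing failures. So S_k ≥ S at every time. One minus Kaplan-Meier is never lower, and it is higher as soon as a competing failure precedes a later event of interest.

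**Inputs.** Two-year PFS is 65% (null) or 81% (alternative), with 45 evaluable patients, 2 years of accrual and 1 further year of follow-up (Section 10.2). The null annual hazard is .215 (Section 10.5). The share s of PFS events that are the recurrence type of interest is an assumption, taken from 0.2 to 0.9, because the documents give no split for this population.

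**The plan's own figures.**
- h0 = −ln(0.65)/2 = 0.2154, which agrees with .215. h1 = −ln(0.81)/2 = 0.1054.
- Expected events with uniform accrual, 45 × [1 − (e^(−h) − e^(−3h))/(2h)]: 15.52 under the null and 8.48 under the alternative.
- Power on the log-hazard scale at one-sided 0.10: Φ{[ln(h0/h1) − 1.2816/√15.52] × √8.48} = Φ(1.135) = 87.2%, against the stated 87%.

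None of these uses the component curves.

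**Size, with all other first failures competing.** With constant cause-specific hazards that sum to h:
- one minus Kaplan-Meier = 1 − exp(−s·h·t)
- cumulative incidence = s × [1 − exp(−h·t)]

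For s = 0.5 at 65% and 2 years: 1 − √0.65 = 19.4%, against 0.5 × 0.35 = 17.5%.

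| 2-year PFS | Years | s | 1 − KM (%) | Cumulative incidence (%) | Excess (points) |
|---|---|---|---|---|---|
| 65% | 2 | 0.2 | 8.3 | 7.0 | 1.3 |
| 65% | 2 | 0.5 | 19.4 | 17.5 | 1.9 |
| 65% | 2 | 0.9 | 32.1 | 31.5 | 0.6 |
| 65% | 3 | 0.2 | 12.1 | 9.5 | 2.6 |
| 65% | 3 | 0.5 | 27.6 | 23.8 | 3.8 |
| 65% | 3 | 0.9 | 44.1 | 42.8 | 1.3 |
| 81% | 2 | 0.2 | 4.1 | 3.8 | 0.3 |
| 81% | 2 | 0.5 | 10.0 | 9.5 | 0.5 |
| 81% | 2 | 0.9 | 17.3 | 17.1 | 0.2 |
| 81% | 3 | 0.2 | 6.1 | 5.4 | 0.7 |
| 81% | 3 | 0.5 | 14.6 | 13.5 | 1.1 |
| 81% | 3 | 0.9 | 24.8 | 24.4 | 0.4 |

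The excess is largest near s = 0.5. If the curves were carried to the 5-year visits of Section 8.4 at the same hazards, its maximum would be 8.7 points at 65% and 2.7 points at 81%.

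**What the existing clause would repair.** Take an illustrative split of 25% local, 25% regional, 35% distant and 15% death without recurrence, at 65% and 2 years.
- Local recurrence by one minus Kaplan-Meier: 1 − exp(−0.25 × 0.4308) = 10.2%.
- Adjusted for death only: (0.25/0.40) × [1 − exp(−0.40 × 0.4308)] = 9.9%.
- With all other first failures competing: 0.25 × 0.35 = 8.75%.

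The death clause removes about 0.3 of the 1.5 points. Across three such splits, with death at 10 to 20% of events and PFS at 65% or 81%, a death-only adjustment changes the local estimate by 0.1 to 0.3 points at 2 years and 0.1 to 0.7 at 3 years.

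**The case against.** The strongest reply is that the plan already recognises competing risks, names cumulative incidence and gives a trigger. For death that is fair: what remains is the permissive wording. It does not reach other first failures, as the split above shows.

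The effect is also small against sampling error. At 17.5% with 45 patients the standard error is √(0.175 × 0.825/45) = 5.7 points before censoring, a 95% half-width of about 11 points. The largest 2-year excess, 1.9 points, is 0.94 of a patient in 50. This stands and sets the weight of the point. The excess is nevertheless systematic and avoidable.

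Third, Section 8.4 only permits assessments to stop, and it asks for tissue if recurrence is pathologically documented at any time. Section 5.7 keeps patients monitored after treatment ends for progression. Some local recurrences after distant failure will therefore be seen. That makes the curves depend on local practice, which is a further reason to fix the rule.

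Fourth, distant failure counts as progression, and no listed objective asks for a separate curve. Adding one is a recommended extension rather than the repair of a contradiction.

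Three stronger readings are tempting but unsupported:
- *The estimates will be too high in every realisation of the trial.* The two estimators coincide when no competing failure precedes a later event of interest. That is possible with about 8.5 expected PFS events under the alternative.
- *These rates would feed the later randomised trial.* Section 2.1 ties the estimates for that trial to 2-year PFS.
- *The curves fail to add up to one minus PFS.* The Section 10.4 list includes death from any cause, which can follow recurrence. The listed curves are not exclusive first events, so they would not sum to that total even if each were estimated perfectly.

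**Conclusion.** The point holds as a modest defect in a descriptive analysis. As written, the rule gives local and regional recurrence rates that are never below the true cumulative incidence, and above it whenever a competing failure precedes a later event of interest. Using the optional death adjustment in full would leave most of the excess in the illustrative split above.

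For shares of 0.2 to 0.9 the excess is 0.6 to 1.9 points at 2 years and 1.3 to 3.8 points at 3 years at 65% 2-year PFS. At 81% it is 0.2 to 0.5 and 0.4 to 1.1 points. Three years is the longest follow-up under the planned accrual and follow-up in Section 10.2.

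These sizes rest on constant cause-specific hazards, on the assumed shares, and on other first failures being censored in the recurrence curves. Kaplan-Meier is correct for death. Local and regional recurrence are not listed objectives, and the PFS test, the sample size and the futility rule do not change.

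**What to change.** In Section 10.4:
- Make cumulative incidence (Aalen-Johansen) with 95% confidence intervals the pre-specified estimator for local and regional recurrence as first failure, with the other first failures and death as competing events.
- Add distant failure to the list on the same basis.
- Keep Kaplan-Meier for PFS and overall survival.
- Remove the *if needed* condition and the *may* in the later sentence on intervening deaths.
- State how a patient is classified when two sites of failure are found at the same assessment.

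The cost is about one sentence for the estimator and one for simultaneous failures. The method is in standard software. Neck and chest imaging is already scheduled at each long-term visit (Section 8.4 and the Appendix C calendar), so no new assessments are needed; the site of first failure has to be recorded.

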ISA101 is currently being studied in a company-sponsored Phase 1 trial, CervISA in patients with recurrent or metastatic HPV16+ cervical cancer. The CervISA trial, a Phase 1 dose escalation study, has enrolled 77 subjects as of May 27, 2016, of which 60 are expected to be evaluable for both safety and immunologic responses. In addition to routine safety monitoring and reporting, the sponsor and the Data Monitoring Committee (DMC), have reviewed the emerging safety data on 4 separate occasions, prior to each dose escalation decision and again prior to the amendment to expand the 40 and 100 µg/peptide cohorts. Preliminary safety data were reviewed with a data cut-off of May 31, 2016. The key findings related to the safety of ISA101 in the CervISA trial can be summarized as follows:

- Most of the AEs in the study were expected toxicities reported to be related to chemotherapy or to complications associated with progression of cervical cancer.
- Dose-related local injection site reactions (ISRs) to ISA101 were the most frequent AEs reported to be related to ISA101 with ISRs occurring in most subjects who received ISA101. Most of the local ISRs were reported to be Grade 1 to 2 in severity. One local ISR was reported to be Grade 3 in severity at a dose of 300 µg/peptide. The frequency of ISRs appeared to be dose related. At the 100 µg/peptide dose level (to be used in the bridging study of ISA101b) most of the patients had local ISRs.
- As of May 31, 2016, there have been 4 systemic allergic reactions reported as SAE to possibly related to ISA101. Three of these reactions occurred at a dose level of 300 µg/peptide and were reported to be probably related to ISA101. One of these events was reported as Grade 4 and the others were reported to be Grade 3. In addition there was one report of a Grade 3 systemic allergic reaction reported at the 100 µg/peptide dose level, though the event was determined to have occurred within 30 minutes after receiving IV contrast material but 2-3 hours after ISA101. While the temporal relationship to IV contrast material was clear, a relation to ISA101 could not be absolutely excluded so this reaction was reported to be possibly related to ISA101. No additional systemic allergic reactions have been reported to date in the extension cohorts with the addition of 6 patients each at both the 40 and 100 µg/peptide levels.

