5.8.1 DLT

DLT is defined as the occurrence of a severe adverse event (AE) listed below that is *at least possibly* related to ISA101b and pembrolizumab and occurs within 24 weeks of the initiation of ISA101b or pembrolizumab and leads to at least a two week delay in CRT. AEs will be graded according to NCI CTCAE version 5.0. The Data Safety and Monitoring Committee of the H&N Program at UPMC Hillman Cancer Center (HCC) will determine causality and whether to remove the suspension and permit the trial to proceed, in consultation with the Principal Investigator, key co-Investigator(s), ISA and Merck.

DLT Definition:

Since autoimmune/inflammatory events may occur at any time during the course of treatment, and may occur with evidence of clinical benefit, the following criteria will be used to define DLT:

- Any \geq Grade 3 non-hematologic toxicity **except**:
 - Grade 3 in-field radiation dermatitis for which IMRT is held \leq 1 week (5 fractions)
 - Grade 3 mucositis for which IMRT is held \leq 1 week (5 fractions)
 - Asymptomatic Grade 3 hypomagnesemia or hypokalemia, which corrects to Grade \leq 2 with replacement therapy
 - Grade 3 dysphagia
 - Grade 3 pain
 - Grade 3 weight loss
 - Grade 3 fatigue
- An alanine or aspartate amino transaminase elevation of greater than three times the upper limit of normal with concurrent elevation of bilirubin two times the upper limit of normal attributable to pembrolizumab should be considered a DLT. Patients meeting this criterion should be permanently discontinued from pembrolizumab.
- Autoimmune toxicity of any grade requiring systemic corticosteroids or other anti-inflammatory that cannot be tapered off in less than 12 weeks.
- Delay in completion of radiation therapy >10 fractions, or inability to complete prescribed IMRT course, due to immune toxicity at least possibly attributed to pembrolizumab or ISA101b.
- Grade \geq 3 neutropenia with fever (oral temperature $> 39^{\circ}\text{C}$)
- Grade \geq 3 thrombocytopenia with bleeding
- Grade \geq 3 local injection site reaction at the site of ISA101b injection
- Grade \geq 3 systemic allergic following ISA101b injection

Patients who experience a DLT to pembrolizumab will receive no additional doses of pembrolizumab and will be withdrawn from the protocol. Patients who experience a DLT to ISA101b will receive no additional doses of ISA101b but may continue on protocol treatment (cisplatin, IMRT, Pembrolizumab) with PI approval.

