10.1 Objectives

Primary Objective:

To estimate two year progression-free survival of the combination of ISA101b, pembrolizumab and cisplatin-based CRT in intermediate risk HPV positive patients and to decide if the outcome warrants further investigation of the combination when compared to the current standard of care (CRT) for this patient population.

Secondary Objective:

- To evaluate the toxicity of the combination of pembrolizumab and ISA101b and concurrent cisplatin-IMRT in patients with PULA HPV-16+ “intermediate risk” HNSCC

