12. ASSESSING AND REPORTING ADVERSE EVENTS

12.1 Definition of Adverse Event

Adverse event means any untoward medical occurrence associated with the use of the drug in humans, whether or not considered drug related.

Suspected adverse reaction. Any adverse event for which there is a reasonable possibility that the drug caused the adverse event (considered "possibly related"). For the purposes of safety reporting, "reasonable possibility" means there is evidence to suggest a causal relationship between the drug and the adverse event. Suspected adverse reaction implies a lesser degree of certainty about causality than adverse reaction, which means any adverse event caused by a drug.

Adverse reaction means any adverse event caused by a drug. Adverse reactions are a subset of suspected adverse reactions where there is reason to conclude that the drug caused the event.

Serious Adverse Event: Any untoward medical occurrence associated with the use of a drug in humans, whether or not considered drug related. Specifically, results in death, is life-threatening, requires inpatient hospitalization or causes prolongation of existing hospitalization, results in persistent or significant disability/incapacity, is a congenital anomaly/birth defect, or is an important medical event (defined as a medical event(s) that may not be immediately life-threatening or result in death or hospitalization but, based upon appropriate medical and scientific judgment, may jeopardize the subject or may require intervention [e.g., medical, surgical] to prevent one of the other serious outcomes listed in the definition above.) Any subject death within 30 days of the last dose of study drug, regardless of the causality or a secondary malignancy should also be recorded as a serious adverse event.

Life-threatening, suspected adverse reaction. A suspected adverse reaction is considered "life-threatening" if, in the view of either the Investigator (i.e., the study site principal investigator), its occurrence places the patient or

research subject at immediate risk of death. It does not include a suspected adverse reaction that had it occurred in a more severe form, might have caused death.

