12.4.1 Serious Adverse Events

A serious adverse event is any adverse event occurring at any time during protocol treatment with ISA101b,, pembrolizumab, cisplatin and IMRT that:

- Results in death;
- Is life threatening;
- Results in persistent or significant disability/incapacity;
- Results in or prolongs an existing inpatient hospitalization (NOTE: Elective outpatient procedures for feeding tube placement do not constitute SAEs in this protocol.)
- Is a congenital anomaly/birth defect;
- Is a new cancer (that is not a condition of the study);
- Is associated with an overdose;
- Is another important medical event

Refer to Table 13 below for additional details regarding each of the above criteria.

For the time period beginning when the first dose is administered, until 90 days after last dose, any serious adverse event, or follow up to a serious adverse event, including death due to any cause that occurs to any subject must be reported within 24 hours to the Sponsor and within 2 working days to Merck Global Safety and ISA using the CRS departmental SAE form if it causes the subject to be excluded from the trial, or is the result of a protocol-specified intervention, including but not limited to washout or discontinuation of usual therapy, diet, placebo treatment or a procedure.

For the time period beginning when the first dose is administered through 90 days following cessation of treatment, or 30 days following cessation of treatment if the subject initiates new anticancer therapy, whichever is earlier, any serious adverse event, or follow up to a serious adverse event, including death due to any cause whether or not related to pembrolizumab, must be reported within 24 hours to the Sponsor and within 2 working days to Merck Global Safety and ISA using the departmental SAE form. Elective outpatient procedures for feeding tube placement do not require expedited Adverse Event Reporting.

Non-serious Events of Clinical Interest will be forwarded to Merck Global Safety and to ISA, and will be handled in the same manner as SAEs.

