Record one of the following	Use the following scale of criteria as guidance (not all criteria must be present to be indicative of pembrolizumab relationship).	
Yes, there is a reasonable possibility of pembrolizumab relationship.	There is evidence of exposure to pembrolizumab. The temporal sequence of the AE onset relative to the administration of pembrolizumab is reasonable. The AE is more likely explained by pembrolizumab than by another cause.	
No, there is not a reasonable possibility of pembrolizumab relationship	Subject did not receive pembrolizumab OR temporal sequence of the AE onset relative to administration of pembrolizumab is not reasonable OR there is another obvious cause of the AE. (Also entered for a subject with overdose without an associated AE.)	
Consistency with Trial Treatment Profile	Is the clinical/pathological presentation of the AE consistent with previous knowledge regarding ISA11b or class pharmacology or toxicology as described in the ISA101b Investigator Brochure?	
The assessment of relationship will be reported on the case report forms /worksheets by an investigator who is a qualified physician according to his/her best clinical judgment, including consideration of the above elements.		
Record one of the following	Use the following scale of criteria as guidance (not all criteria must be present to be indicative of ISA101b relationship).	
Yes, there is a reasonable possibility of ISA101b relationship.	There is evidence of exposure to ISA101b. The temporal sequence of the AE onset relative to the administration of ISA101b is reasonable based on the information in the ISA101b Investigator Brochure. The AE is more likely explained by ISA101b than by another cause.	

No, there is not a reasonable possibility of ISA101b relationship	Subject did not receive ISA101b OR temporal sequence of the AE onset relative to administration of ISA101b is not reasonable OR there is another obvious cause of the AE. (Also entered for a subject with overdose without an associated AE.)
--	--

Timelines for Reporting of Suspected Adverse Events

All events meeting the definition of a serious adverse event should be reported according to the departmental SAE checklist and SAE form. Serious adverse events are collected from the date of the subject's first dose of treatment until 90 days after the final dose. The initial SAE form should be sent to the following within 24 hours/1 business day of the Sponsor-Investigator becoming aware:

1. [name]

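### The only end-of-study toxicity summary is limited to treatment-related events; an all-cause table by grade should be added

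*Combined protocol and SAP*

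**What the plan says.** Section 10.4 states: "Treatment-related toxicities will be summarized by frequency and grade". It adds nothing on which treatment is meant, which patients form the denominator, or over what period.

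Section 10.1 (and 2.2) gives a single secondary objective: "To evaluate the toxicity of the combination of pembrolizumab and ISA101b and concurrent cisplatin-IMRT". It is not confined to events judged related. The opening of Section 10 adds that the study should characterise the safety profile of the combination.

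Section 12.1 has all observed or volunteered events, serious or not, entered in the case histories whatever their suspected cause, with enough information to assess causality. Table 14 then asks a qualified physician for a Yes or No on a reasonable possibility of relationship, separately for pembrolizumab and for ISA101b. Cisplatin and IMRT are to be taken into account in that judgement.

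The other safety outputs are the dose-limiting toxicity and treatment-delay monitoring (Sections 5.8 and 10.3), expedited reporting of serious events (Section 12.4.1), and committee oversight reports (Section 13).

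**The concern.** In a single-arm trial there is no concurrent group whose event rate shows what chemoradiation alone would have produced. A count of related events stands in for that comparison, and it is only as good as the individual causal calls. Investigators here know the treatment (Section 11.3), and four components overlap in time and in harms. An all-cause table does not depend on those calls. The plan collects the data for one but does not commit to producing it.

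What is at stake is the interpretation of the safety result. Section 2.1 looks ahead to a definitive randomized trial. Those planning it would receive toxicity rates already filtered by judgement, without the unfiltered rates needed to compare with other chemoradiation series.

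**Working it through.** The plan gives no figure on this point, so the check sets its provisions side by side.

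1. **Objective against analysis.** The objective in 10.1 is the toxicity of the combination, including cisplatin-IMRT. The analysis in 10.4 covers only events judged treatment-related. The analysis is narrower than the objective.

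2. **Collection against analysis.** Section 12.1 collects events irrespective of suspected cause. No section plans a table of them by grade at the end of the study.

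3. **Where attribution is hard.** Hypothyroidism is an immune-related event of pembrolizumab in Table 4 (Section 5.4.1) and a long-term effect of radiation in Section 5.5.13. Renal toxicity appears as nephritis in Table 4 and as a cisplatin effect in Section 7.3.

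4. **Tracing two hypothetical events.** Event A is a Grade 3 creatinine rise in week 4, after cisplatin in weeks 0 and 3 and pembrolizumab in weeks -1 and 2 (Table 2). Event B is a pulmonary embolism in month 4 that the investigator ascribes to the cancer.

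| Table produced | Event A | Event B |
|---|---|---|
| All causes | counted | counted |
| Related to any of the four components | counted | not counted |
| Related to ISA101b or pembrolizumab only | depends on judgement | not counted |

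For Event A under the agent-only reading, Table 14's guidance for Yes includes, for the vaccine, "The AE is more likely explained by ISA101b than by another cause", with a parallel line for pembrolizumab. No applies where "there is another obvious cause of the AE". Cisplatin is an obvious candidate, so two careful physicians could record opposite answers. Event B disappears from any related-only table, whichever reading is used. Only the all-cause row gives the same count for both events whoever does the attributing.

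5. **Whether another output fills the gap.** Section 12.4.1 defines a serious event without reference to cause, as "any adverse event occurring at any time during protocol treatment with ISA101b,, pembrolizumab, cisplatin and IMRT" that meets a seriousness criterion. That covers serious events only and serves expedited reporting. Section 13 provides summaries of serious events to the IRB at renewal. Section 10.3 counts treatment delays. None is an end-of-study table of all events by grade.

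6. **Size.** The distortion depends on the proportion of events in this regimen that investigators would call unrelated. The documents give no such proportion, so no estimate is offered.

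**The case against.** The strongest reply is that context largely settles what treatment-related means. Two sentences earlier, 10.4 refers to the whole treatment regimen. Section 5 lists all four components, and the objective concerns the full combination. Where the plan wants agent-only attribution it names the agents, as in 5.8.1: "due to immune toxicity at least possibly attributed to pembrolizumab or ISA101b". On that reading the summary loses only events ascribed to none of the four components, and most overlapping harms are counted whichever component is blamed. Most of this stands, and it limits the likely effect. It does not remove the filter: events like B above are still dropped on individual judgement. It is also unclear that an any-component answer is recorded. Table 14 gives Yes or No categories for the two agents only. However, its row heading names cisplatin and IMRT, and Section 8.2 schedules toxicity assessment with attribution. The case report forms are not in the documents.

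Three stronger readings are tempting, and the documents do not support them.

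- **That the plan has several conflicting definitions of relatedness.** Section 12.1 defines a suspected reaction by reasonable possibility, equates this with possibly related, and explains that the phrase "means there is evidence to suggest a causal relationship between the drug and the adverse event". Section 5.8.1 uses the same possibly-related level, and Table 14's Yes is worded as reasonable possibility. The more-likely-explained line is guidance, and not every item of that guidance has to be met. There is one threshold, with some room for stricter application in Table 14.

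- **That the allergic reaction described in Section 1.6.2 can size the effect.** It followed IV contrast within 30 minutes and ISA101 by 2-3 hours, and "a relation to ISA101 could not be absolutely excluded so this reaction was reported to be possibly related to ISA101". Calling it No under Table 14 would be a guess: exposure was certain, and the onset lies inside the 4-hour observation period of Section 5.4.2. Nor can the event be matched to a denominator, because Appendix D lists hypersensitivity only in the 300 µg plus INF column.

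- **That late toxicity is left out.** Section 10.4 sets no time window, and Appendix C continues adverse event evaluation in long-term follow-up. Whether late events have a separate table by visit is a presentation choice.

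**Conclusion.** The point holds as a minor one. The only planned end-of-study toxicity analysis is restricted to events judged treatment-related, although the objective is the toxicity of the whole combination and all-cause data are collected. The reported rates will therefore depend on attribution in an uncontrolled, open-label setting. The effect is probably small under the any-component reading and larger under an agent-only reading; the documents do not allow a number for either.

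This assumes that 10.4 is applied as written and that no fuller table plan exists outside the documents. A reader might infer that patient safety oversight or the efficacy conclusion is weakened. Neither follows: the dose-limiting toxicity rules, the delay monitoring, the suspension rule for possibly related deaths and the one-sided PFS test do not use this summary.

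**What to change.** Replace the toxicity sentence in Section 10.4 with:

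> All adverse events from the first dose of study treatment, regardless of attribution, will be summarised by term and worst CTCAE v5.0 grade in all patients who receive any study treatment. Events with a reasonable possibility of relationship to ISA101b or pembrolizumab (Table 14 Yes) will be tabulated as a subset.

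This names the denominator, which 10.4 leaves open, and ties the related subset to a category that Table 14 already asks physicians to record. No new data collection is needed. The cost is protocol wording and a few more tables. The headline rates will look less favourable than an agent-only summary, because they will include expected chemoradiation events, such as the Grade 3 mucositis or dysphagia that Section 5.5.13 anticipates in about one third to one half of patients. The subset table keeps the agent-specific picture visible alongside them.
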